Diagnosis and main criteria for inclusion	
 ▪ Men or women aged 18 years and older, inclusive ▪ Systemic Sclerosis as defined by 2013 the American College of Rheumatology (ACR) / European League Against Rheumatism (EULAR) classification. ▪ Steady daily doses of any immunosuppressive medication, vasodilators, antidepressants and anxiolytic use for 4 weeks prior to baseline. ▪ PROMIS-fatigue score of at least 45 ▪ Currently owns and operates a smart phone regularly ▪ Ability to provide informed consent
Study Design	Open label, single-arm, single center US study
Type of control	None
Number of participants	30
Primary outcome variable	Change in the PROMIS-Fatigue scale at four weeks

30

Plan for statistical analysis

The planned sample size of 30 SSc participants is based on practical considerations to obtain estimates of the magnitude of treatment differences for efficacy and safety rather than a desired power for a pre-specified difference.

From similar studies on Rheumatoid Arthritis and Systemic Lupus Erythematosus, the improvement of T-score after treatment is about 5. The standard deviation for general population is 10. However, we are restricting our population to participants with fatigue T-scores of less than 54 (with low score indicating high fatigue). With the range of T-score reduced about half, we expect the standard deviation to be about 5. The effect size is expected to be 1 (5/5).

Using paired t-test, we have 86% power to detect the effect size of 1 when we recruit 30 patients at a significance level of 0.05. We asked the IRB for the option of increasing the number of patients to 40, which will give us about 81% power to detect a smaller effect size of 0.8 at a significance level of 0.05.

Descriptive statistics will be derived for all clinical variables, mean and standard deviation for continuous outcomes and percentages for categorical and dichotomous variables.

The primary outcome of interest is fatigue, as measured by the FACIT-Fatigue. We will compare the mean change from baseline and four weeks in a repeated measures model.

The p-values resulting from formal statistical tests will be interpreted from a hypothesis-generating, rather than a confirmatory framework.

Table of contents

1. Introduction	9
1.1 Background	9
1.1.1 Scleroderma (systemic sclerosis).....	9

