4. STUDY DESIGN

4.1 Design overview

This clinical trial is a single-center, open-label, single-arm study of 30 individuals with SSc and fatigue.

The study will allow for subjects to continue standard of care medications for the management of SSc as background therapy.

The study design consists of a single, four-week intervention. The screening and baseline visits can be combined when the screening is not able to be performed over the phone in advance.

- **Screening phase:** up to 4 weeks prior to baseline visit
- **Observation period:** During this one week phase participants will track their daily Raynaud attack frequency and duration using a diary. This will occur in the seven days preceding the baseline intervention phase.
- **Open-label intervention phase:** This consists of a four-week period during which participants will use the Apollo wearable system as needed to manage symptoms including fatigue. During the intervention phase participants may use the wearable at their discretion and control. Participants will track their daily Raynaud attack frequency and duration using a diary during week 4 of Apollo use. Participants will complete questionnaires on day 1 of the open-label and intervention phase, and at their follow-up four weeks later.

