4.1.1 Screening phase (up to 4 weeks prior to baseline visit)

After providing written informed consent, participants will undergo a screening evaluation to determine their eligibility (see Section [7.1](#) for a detailed schedule of events). Participants will complete the PROMIS-Fatigue scale to determine if they have moderate to severe fatigue. If a T score of 45 is obtained, and all inclusion criteria are met, then the patient may proceed to the observation phase. Participants will be given the 7-day diary to be completed starting one week prior to their scheduled baseline visit. They will be reminded by telephone call or text (based on

their preference) to begin their diary collection.

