5.1 Eligibility

5.1.1 Inclusion criteria

Participants must meet the following criteria to be eligible for enrollment in the study:

1. Signed written informed consent
2. Men or women aged 18 years and older
3. Diagnosis of Systemic sclerosis, as defined by 2013 American College of Rheumatology/ European Union League Against Rheumatism classification of SSc.
4. Baseline T score of 45 on the PROMIS-Fatigue scale.
5. Steady daily doses and any immunosuppressive medication, vasodilators, antidepressants and anxiolytic use for 4 weeks prior to baseline.
6. Currently owns and operates an iOS or Android smart phone regularly
7. Ability to comply with the clinical visits schedule and the study-related procedures.
8. Subjects who have struggled with symptoms of SSc (specifically fatigue and Raynauds) who have not received adequate symptom relief from prior treatment attempts (treatment-resistant) will be prioritized.
- 9.

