7.1.2.2 Visit 1 – Baseline

The following assessments will be performed at the Baseline visit

- Reconfirmation of eligibility
- PROMIS-fatigue scale administered
- Patient reported outcomes (QUIDS-SR, patient global assessment, PROMIS-29, HAQ-D1/SHAQ, visual analog scales) and physician global assessment
- Vital signs (blood pressure and heart rate). The blood pressure is measured in a sitting

position after the participant has been at rest for at least 5 minutes. The same arm is always used for these measurements

- Digital ulcer assessment
- Assessment of Raynaud attacks – participant provided the one-day diary and RCS to complete the day following the screening
- Recording and assessment of AEs (see Section [7.5.1.3](#))
- Downloading of the mobile application and teaching of how to use the Apollo wearable device. The participants will be allowed to use it up to 30 minutes to familiarize themselves with the working of the device while at this visit.

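### Combined screening and baseline visits let the qualifying fatigue score serve as the baseline, so regression to the mean can enter the uncontrolled primary change

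*Combined protocol and SAP*

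**What the plan says.** **Visits.** Section 4.1 of the protocol allows the first two visits to be merged: "The screening and baseline visits can be combined when the screening is not able to be performed over the phone in advance".

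**Where the cut is applied.** Section 4.1.1 places it at screening: "Participants will complete the PROMIS-Fatigue scale to determine if they have moderate to severe fatigue", and then "If a T score of 45 is obtained, and all inclusion criteria are met, then the patient may proceed to the observation phase". Criterion 4 in Section 5.1.1 reads "Baseline T score of 45 on the PROMIS-Fatigue scale". Section 7.1.2.2 lists "Reconfirmation of eligibility" at Visit 1, beside a new administration of the scale. The schedule of events marks PROMIS-Fatigue at screening, baseline and week 4, but the list of screening procedures in Section 7.1.2.1 omits it. Nothing says which score is the baseline when the visits are merged, or that two scores are then needed.

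**Direction of the cut.** The synopsis requires a "PROMIS-fatigue score of at least 45" among its inclusion criteria, but its statistical plan speaks of "participants with fatigue T-scores of less than 54 (with low score indicating high fatigue". Section 4.1.1 and criterion 4 give 45 with no direction.

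**Endpoint.** The primary outcome is the within-person change in PROMIS-Fatigue from baseline to four weeks (Sections 2 and 7.3) in a single-arm study (Section 6.2). The synopsis expects an improvement of about 5 T-score points and gives 10 as the general-population SD.

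**Diary.** Section 4.1 includes a one-week Raynaud diary: "This will occur in the seven days preceding the baseline intervention phase". Section 4.1.1 hands it out at screening. Section 4.1.2 lets participants use the device once they leave the baseline visit. Sections 2.1, 7.1.2.2 and the last paragraph of 7.6.1 describe a one-day diary instead.

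**The concern.** A person admitted because one measurement passed a threshold tends, on average, to score closer to the population mean next time, even if nothing has changed. When that same measurement is the baseline of a before-after comparison, the drift becomes part of the estimated effect. A control arm would cancel it; this trial has none. The reference in Section 8.2.2 to two treatment groups does not supply one.

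What is at stake is the size of the primary estimate, which is the stated purpose of the study (synopsis and Section 8.5). The plan does not mention regression to the mean, and the observation week collects only Raynaud data, so it provides no second fatigue score.

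A merged visit also leaves no room for the seven-day diary before the device goes home. The one-day form in Section 7.1.2.2 does not help, because it falls on the day after screening, which for these participants is after handover. Their Raynaud diary outcomes would then have no pre-device baseline.

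**Working it through.** The plan states no figure for this effect, so there is none to reproduce.

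**Inputs from the documents.** Cut 45, taken as a floor (synopsis inclusion criteria); SD 10 (synopsis, general population); expected improvement 5 points; n = 30; two-sided 5% test (Section 8.1).

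**Assumptions, because the documents are silent.** Normally distributed scores; high score means more fatigue; screened mean 50, 55 or 60; correlation r between two occasions of 0.7 to 0.9; no device effect.

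**Step 1: the qualifying score is the baseline.** With c = (45 − mean)/10, the expected spurious improvement is 10 × (1 − r) × λ, where λ = φ(c)/(1 − Φ(c)).

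| Screened mean | c | λ | r = 0.7 | r = 0.8 | r = 0.9 |
|---|---|---|---|---|---|
| 50 | −0.5 | 0.3521/0.6915 = 0.509 | 1.53 | 1.02 | 0.51 |
| 55 | −1.0 | 0.2420/0.8413 = 0.288 | 0.86 | 0.58 | 0.29 |
| 60 | −1.5 | 0.1295/0.9332 = 0.139 | 0.42 | 0.28 | 0.14 |

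Simulation agrees with these values. Against 5 points, means of 55 to 60 give 0.14/5 = 3% to 0.86/5 = 17%; the corner at mean 50 and r = 0.7 gives 1.53/5 = 31%. At r = 0.5 the three means give 2.55, 1.44 and 0.69.

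**Step 2: effect on the trial mean.** Multiply by the share of combined visits. If a third were combined (an assumption), this route adds 0.14/3 = 0.05 to 0.86/3 = 0.29 points at means 55 to 60, and 1.53/3 = 0.51 at mean 50 with r = 0.7.

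**Step 3: the test, if all 30 were combined.** In simulation (20,000 runs, no device effect) the paired t-test declares an improvement in 3.5% to 8.7% of trials at means 55 to 60, and in 8.6% to 18.8% at mean 50, against a nominal 2.5%.

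**Step 4: separate visits, with the cut applied again to the Visit 1 score.** With r constant across occasions, the simulated bias is 0.31 to 1.06 points at mean 50, 0.18 to 0.62 at 55 and 0.09 to 0.32 at 60.

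**Step 5: separate visits, with the cut on the screening score only.** If the correlation is the same between all pairs of occasions, the bias is 0.0. If it decays (r between neighbouring occasions, r² between screening and week 4), the bias is 10 × r(1 − r) × λ, which is r times the Step 1 value. At mean 55 and r = 0.7 that is 10 × 0.21 × 0.288 = 0.60, against 0.86. Over r = 0.7 to 0.9 the range is 0.1 to 0.6 points at means 55 to 60, and up to 1.1 at mean 50.

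**Step 6: direction.** A ceiling of 54 with low scores meaning fatigue also favours the device: 0.16 to 1.69 points over assumed means of 40 to 50. A floor of 45 with low scores meaning fatigue, which is what results if the two synopsis statements are read together literally, gives the Step 1 sizes against the device.

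**The case against.** The strongest reply is that the usual pathway is already sound. Section 4.1.1 applies the cut at screening, the schedule gives a fresh score at baseline, and merging is for people who could not be screened by phone. Section 7.1.2.2 lists the eligibility check and the questionnaire as separate items and does not say that the cut is applied again. This stands in part: re-selection at a separate Visit 1 is one reading, resting on the word baseline in criterion 4 and on the eligibility check. A reader might infer that it is certain; the documents do not settle it.

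The size can also be challenged. A reader might take about 30% of the expected effect, or a false-positive rate near 19%, as the likely consequence. Both need a screened mean of 50 and r = 0.7, and the 19% needs all 30 visits combined. A mean of 50 suits a population no more fatigued than the one assumed for the scale, whereas Section 1.1.2 says that fatigue is more prevalent in systemic sclerosis than in the general population and criterion 8 gives priority to patients with unrelieved fatigue. Means of 55 to 60 are the better guide, though they too are assumed.

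Finally, p-values here are meant to generate hypotheses (Section 8.1). That lowers the weight of Step 3, but it does not excuse bias in the estimate that the study exists to provide.

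**Conclusion.** The point holds as a modest, avoidable bias. The plan permits one score to both qualify a participant and start the primary change, and it has no means of separating regression to the mean from device effect. Under the stated assumptions the bias is about 0.1 to 0.9 points per combined participant at screened means of 55 to 60, and up to 1.5 at a mean of 50. Its effect on the trial mean scales with a share of combined visits that the plan does not give.

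A reader might infer that the bias must always favour the device. That follows only if the cut selects the fatigued end, which Section 4.1.1 intends. The synopsis contradicts itself on scale direction, and one literal combination reverses the sign. Those passages must be reconciled.

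The conflict between a combined visit and the seven-day pre-baseline diary needs no assumption about scores. It affects the secondary Raynaud outcomes, not the primary endpoint.

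**What to change.** 1. Reword criterion 4 so that the cut applies to the screening score only, and state that the Visit 1 PROMIS-Fatigue score is not used to re-select. Give the cut an explicit direction in criterion 4 and Section 4.1.1, reconciled with both statements in the synopsis. Add PROMIS-Fatigue to the screening list in Section 7.1.2.1.
2. Hold Visit 1 separately, after the seven-day observation period, with a fresh PROMIS-Fatigue completed before the device is handed over. Reconcile the seven-day and one-day diary texts at the same time.
3. If combined visits are kept, record which participants had them and prespecify a sensitivity analysis of the primary change without them.

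The cost is protocol wording and one extra trip for those not screened by phone, a gap that the diary week already requires. Some participants will have a Visit 1 score on the other side of the cut; that has to be accepted, because excluding them brings the selection back.

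This removes regression to the mean from the primary change if the correlation between occasions is constant. Otherwise it only reduces it: under the decay pattern in Step 5, 70% to 90% of the Step 1 bias remains for r of 0.7 to 0.9. Placebo response and natural change stay in any uncontrolled estimate and should be named as limits when it is reported.

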4.1.1 Screening phase (up to 4 weeks prior to baseline visit)

After providing written informed consent, participants will undergo a screening evaluation to determine their eligibility (see Section [7.1](#) for a detailed schedule of events). Participants will complete the PROMIS-Fatigue scale to determine if they have moderate to severe fatigue. If a T score of 45 is obtained, and all inclusion criteria are met, then the patient may proceed to the observation phase. Participants will be given the 7-day diary to be completed starting one week prior to their scheduled baseline visit. They will be reminded by telephone call or text (based on

their preference) to begin their diary collection.

4.1.2 Intervention Phase

At the baseline visit, participants who have met all of the inclusion criteria. At this visit they will complete the following questionnaires:

- 1) PROMIS-fatigue
- 2) PROMIS-29
- 3) The QUIDS-SR
- 4) HAQ-DQ with SHAQ
- 5) Raynaud condition score, Raynaud visual analog scale and digital ulcer visual analog scale

They will then be provided the wearable Apollo system device. They will download the mobile application, and be taught how to install it and use it to control the wearable Apollo device by the research coordinator(s). Any questions will be answered at this time. Participants will be able to use the device from the time they leave the visit. Use of the device will be entirely at the subject's control.

In the week prior to their end-of-study visit, participants will complete a daily diary collection of Raynaud attack episodes and symptoms using the paper diary form. This will be provided prior to leaving the baseline visit.

Participants will be sent a reminder call or text the day before and day they are to begin their diary collection on one week prior to their scheduled end-of-study visit.

4.1.3 Early Termination

If participants choose to discontinue using the device, they may remain in the study, and will be requested to return for the four-week follow-up visit and complete all questionnaires.

5. Study population

5.1 Eligibility

5.1.1 Inclusion criteria

Participants must meet the following criteria to be eligible for enrollment in the study:

1. Signed written informed consent
2. Men or women aged 18 years and older
3. Diagnosis of Systemic sclerosis, as defined by 2013 American College of Rheumatology/ European Union League Against Rheumatism classification of SSc.
4. Baseline T score of 45 on the PROMIS-Fatigue scale.
5. Steady daily doses and any immunosuppressive medication, vasodilators, antidepressants and anxiolytic use for 4 weeks prior to baseline.
6. Currently owns and operates an iOS or Android smart phone regularly
7. Ability to comply with the clinical visits schedule and the study-related procedures.
8. Subjects who have struggled with symptoms of SSc (specifically fatigue and Raynauds) who have not received adequate symptom relief from prior treatment attempts (treatment-resistant) will be prioritized.
- 9.

5.1.2 Exclusion Criteria

Participants who meet any of the following criteria will be excluded from enrollment in the study:

1. Medical and surgical history
 - Major surgery within 8 weeks prior to screening
 - Participants with an active malignancy.
 - End-stage renal disease with an estimated glomerular filtration rate (eGFR) $< 15 \text{ mL/min/1.73m}^2$ (MDRD formula) or on dialysis at the screening visit
 - Hepatic insufficiency as defined by the Child-Pugh criteria
 - Hospitalization for any reason within four weeks of the study baseline visit.
 - History of sympathectomy or stellate ganglion block
 - Significant interstitial lung disease with FVC $\leq 50\%$ of predicted, or DLCO (uncorrected for hemoglobin) $\leq 40\%$ of predicted
 - Pulmonary hypertension with change in medications in the preceding four weeks
 - Actively prescribed standing doses of beta-blockers.
 - Actively prescribed standing doses of sedatives, hypnotics, opioids, or benzodiazepines.
 - Active or unstable psychotic disorder requiring current prescriptions of standing doses of antipsychotic medications
 - Active suicidal/homicidal ideation or a suicide or homicide attempt in the past year.
2. Pregnant or breastfeeding women
3. Other
 - Any other condition or therapy that would make the participant unsuitable for this study and will not allow participation for the full planned study period

5.1.3 Justification of selection criteria

The selection criteria were carefully selected to exclude participants from the study who may have another significant underlying medical condition contributing to fatigue.

5.2 Withdrawal of participants from study

5.2.1 Withdrawal

Participants *may* be withdrawn from the study at their own request or at the request of their legally acceptable representative. At any time during the study and without giving reasons, a participant may decline to participate further.

6. Intervention

6.1 Intervention to be administered

The Apollo System offers a convenient novel non-invasive, non-habit-forming wearable solution to improve performance and recovery under stress in children and adults by delivering gentle wave-like vibrations to the body that improve autonomic nervous system tone in near real time (Siegle & Rabin et al., under review). Apollo is about the size of an Apple Watch and can be worn on the ankle, wrist, or arm with two adjustable fabric straps. Apollo vibrations activate touch receptors in the skin and are perceived as safety signals by the brain resulting in decreased stress,

improved recovery, focus, and energy.

In addition to the wearable, Apollo is a software system that curates music for the body, rather than for the ears. The scientific principles guiding the use of Apollo and our mechanistic understanding of its effects on the body are consistent with our understanding of how music and therapeutic touch effect the body to convey feelings of energy, focus, or relaxation by sending safety signals to the emotional cortex (limbic system) in the brain. Similar to music and touch used to facilitate a healing response in the body, there are no known side effects to this type of therapy.

Prior studies of Apollo have demonstrated significant improvements in fatigue and energy in healthy subjects in the real world as well as in subjects with chronic illnesses in clinical trials of Apollo within just a few days of use. Early findings strongly suggest that by improving autonomic tone, Apollo is attenuating biomarkers of persistent unwanted sympathetic activity, such as low heart rate variability (HRV), that over time, correlate with worse prognoses in many chronic illnesses. Low HRV is also a predictive factor in fatigue and poor energy recovery. Not only has Apollo been demonstrated to improve HRV and decrease heart rate, respirations, blood pressure, and other markers of stress when threat is misappropriated, but it also appears to be inducing Meyer wave patterns in the vasculature (study data under analysis), which are known to correspond with nitric oxide release. As such, there is significant reason to believe that Apollo will improve symptoms of fatigue, inflammation, and vascular dysfunction in subjects with SSc.

Storage requirements:

All wearable devices not in use during the trial will be stored at the investigational sites at room temperature in a place inaccessible to unauthorized personnel, i.e. in a locked cabinet. No special storage conditions are required.

6.2 Treatment assignment

This is an open-label, single-arm trial. No randomization or blinding will occur.

6.4.3 Special populations

The Apollo wearable has been used in a wide array of populations. No adjustments need to be made in use or instructions.

6.5 Device use and compliance

The Apollo system including wearable hardware and software will track each subjects' use of Apollo throughout the study. This usage data will be stored in HIPAA-compliant manner and linked to a de-identified study subject ID number.

If a participant reduces or stops use of the Apollo wearable, this data will be recorded. The participant will still complete the two week (end of study) visit and assessment as planned.

7. Procedures and variables

